## 2. Secondary endpoints:

Efficacy endpoint

- Time to symptom-free for sore throat.
- The change from baseline in the severity of cough during treatment period.

Safety endpoint

- Physical examination
- Vital sign

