## VII. Selection criteria

## 1. Main inclusion criteria:

- (1) Male or unpregnant female patients  $\geq 18$  years to  $\leq 79$  years of age, who have the symptoms of fever, sore throat, and cough (match the definition in table 1 to 2 in protocol), by investigator's judgement, with mild to severe symptoms ( $> 20$  mm in each VAS).
- (2) With BMI between 18 to 30 kg/m^2.
- (3) Without a history for alcohol or drug abuse, or other significant organic diseases.
- (4) No history of cancer. Unless no signs of relapse occurred for over 5 years which no anticancer therapies are needed.
- (5) Ability to read and write Chinese, and provide data through questionnaire.
- (6) Ability to understand and comply all procedures of the study, and provide written consent.

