## VIII. Study procedures:

This is a multicenter, parallel, double-blind, randomized, placebo-controlled study. A total of 258 male or unpregnant female outpatient subjects  $\geq 18$  years to  $\leq 79$  years of age will be enrolled into this study (dropout rate 10%). There will be 2 visits in this study. In Visit 1 (Day 1), subjects who have the symptoms of fever, sore throat, and cough (match the definition in table 1 to 3 in protocol), by investigator's judgement will be recruited into the study.

Subjects will be randomized into the RespireAid™ group or placebo group with allocation rate 2:1.

Following to the clinical guideline of NRICM101, subjects in RespireAid™ group will take drug four times daily with 20g oral granule, administered for 5 days. The subjects in placebo group received study drug with the same dose frequency. Other than study drugs, the rescue drug, acetaminophen, will be administered. If subjects have moderate or severe fever, sore throat, he/she could receive one rescue medication (500mg) per 4 hours, up to 6 tablets in total in one day. Subjects will be educated how to use e-dairy. The dairy will be recorded the severity of fever, sore throat, and cough from baseline (Day 1, before use of study drug) to Day 5. The efficacy endpoint will be the improvement of fever, sore throat, and cough, and the safety endpoint will be adverse events after treatment. The study and rescue drugs will be dispensed to subjects and the study staff will teach them how to receive medications. If subjects have persistent fever, unscheduled visits will be arranged to check whether or not they would be suitable to participate into this study. Adverse events will be recorded at Visit 2(Day 8), and the dairy with drug record will be checked.

IX. Concomitant treatment:

1. During study period, the drugs which may impact the efficacy evaluation (i.e. fever, sore throat, and cough) will be prohibited, including
  - (1) Chinese medication other than study drug
  - (2) Western medication other than study drug
    - NSAIDs
    - Acetaminophen
  - (3) Expectorant cough medicines
    - Mucolytics, such as Bromhexine
    - Antitussives, including Opioids (e.g. Codeine, Ethylmorphine, Pholcodine), nonopioids (e.g. Noscapine, Dextromethorphan, Chlophedianol), antihistaminics and Prenoxdiazine
    - Adjuvant antitussives, such as bronchodilators
2. During study period, long-term use of NASIDs, corticosteroids or other immunosuppressive agents will be prohibited.

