3. During study period, antibiotics, COVID-19 or influenza antiviral drugs will be prohibited.
4. During study period, subject could receive other treatments/therapies that are not otherwise prohibited and, in the judgment of the Investigator, are required for proper medical care.

X. Statistics

- 1. Primary hypothesis:  superiority  non inferiority  
 equivalence  other
- 2. Sample size: enrolled 258 subjects  
 evaluable 231 subjects
- 3. Efficacy population:  ITT  PP  other  
 Safety population:  ITT  PP  other: Safety Population
- 4. Statistical method(s) for efficacy/safety evaluations:

Efficacy Evaluation

The primary efficacy endpoint is the “time to symptom-free for fever” which is the days of the symptom-free for fever based on the diary record. The primary endpoint will be analyzed by weighted log-rank test for comparison between RespireAid™ and placebo groups. Kaplan-Meier plot will be drew to present the time to event data. The secondary efficacy endpoint of the “time to symptom-free for sore throat” will be analyzed as the analysis of the primary efficacy endpoint. The change from baseline in the severity of cough during treatment period will be summarized as categorical data with frequency and percentage and analyzed by Chi-square test.

Safety Evaluation

All safety assessments, including AEs, physical examinations (PEs), and vital signs (VS), where indicated, will be presented using descriptive statistics by study groups and time points.

- 5. Planned interim analysis:  yes  no

XI. Please attach flow chart and/or assessment schedule, if available.

Visit	1	2
	Screening/Strat of Treatment	End of Treatment/End of Study/Early withdrawal
Days	1	8
Windows		±2
Informed Consent	X	
Inclusion/Exclusion criteria	X	
Randomization	X	
Medical History	X	
Demographic data	X	
Physical Examination	X	X
Vital Signs	X	X
COVID-19 testing		
Chest X ray	X	
Urine Pregnancy test a	X	
Dispense study drug b	X	

Dispense rescue drug c	X	
Return study drug		X
Return rescue drug		X
e-diary d	X	X
Concomitant Medication	X	X
TEAE	X	X

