
a: If the result of urine pregnancy test is positive, the subject won't be enrolled into the study.
 
b: The study drugs will be given four times daily with 20g oral granule, administered for 5 days.
 
c: The rescue drugs could be given one tablet (500mg) per 4 hours, up to 6 tablets in total in one day.
 
d: E-Dairy card will be recorded before use of study drugs(baseline), Day 1 to Day 5.

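### The chi-square test planned for change in cough severity ignores the order of the severity categories and does not adjust for baseline cough, which costs power on a secondary endpoint

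*Protocol*

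**What the plan says.** Section VI lists, among the secondary efficacy endpoints, "The change from baseline in the severity of cough during treatment period". Section X, item 4 fixes its analysis: it "will be summarized as categorical data with frequency and percentage and analyzed by Chi-square test". No trend, rank, stratified or baseline-adjusted form of the test is named.

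Three other places bear on the choice:

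- **Severity is ordered and varies at entry.** Inclusion criterion 1 admits subjects "with mild to severe symptoms". A VAS in mm is mentioned there, but only as an entry threshold.
- **Baseline cough is recorded.** Section VIII has the diary capture "severity of fever, sore throat, and cough from baseline (Day 1, before use of study drug) to Day 5". Note d to the assessment schedule agrees: "E-Dairy card will be recorded before use of study drugs(baseline), Day 1 to Day 5".
- **The outcome may be binary.** Section VIII also says "The efficacy endpoint will be the improvement of fever, sore throat, and cough", which leaves a yes/no reading open.

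The text at hand does not state the diary scale for cough, the number of change categories or the day compared.

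**The concern.** A chi-square test on a two-arm table treats the categories as nominal. A consistent move towards milder cough counts no more than a patternless difference of the same size. Subtracting baseline is also not the same as adjusting for it: a subject who starts at mild can lose one grade at most, while one who starts at severe can lose three, so part of the spread in the change reflects only where subjects began.

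Cough is one of the three symptoms in the trial's objective and one of only two secondary efficacy endpoints. At stake is the chance of detecting a real effect on it. Type I error and the fever analysis are not at stake.

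**Working it through.** **1. Sample size.** The protocol gives "evaluable 231 subjects", 10% dropout and 2:1 allocation.

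- Evaluable: 231 × 2/3 = 154 and 231 × 1/3 = 77.
- Enrolled: 154/0.9 = 171.1, rounded up to 172; 77/0.9 = 85.6, rounded up to 86; 172 + 86 = 258, the stated figure.

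The protocol states no power or effect size for cough, so there is no planned figure to reproduce for this endpoint.

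**2. Why order is lost.** The statistic is X² = Σ (O − E)²/E on K − 1 degrees of freedom. Permuting the K columns only reorders the sum, so X² and its p-value do not change. A row-mean-score test instead gives the categories ordered scores and compares the two mean scores on 1 degree of freedom. With K = 2 there is no order to use.

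**3. Assumptions for the size of the loss.** None of these is in the protocol:

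- Baseline mean 55, SD 18, limited to 20–100; Day 5 mean 30, SD 22, limited to 0–100.
- Effect 0.3 or 0.4 SD; correlation r = 0.3, 0.5 or 0.7.
- Grades cut at 20/45/70; two-sided 0.05; 154 versus 77; 5,000 replicates.

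**4. Graded diary, power in %, for r = 0.3 / 0.5 / 0.7.**

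| Effect | Categories | Chi-square | Row-mean-score | Row-mean-score stratified by baseline grade |
|---|---|---|---|---|
| 0.3 SD | 3 | 29.8 / 36.6 / 50.5 | 36.4 / 45.7 / 59.7 | 45.5 / 53.4 / 64.8 |
| 0.3 SD | 4 | 27.9 / 33.9 / 47.3 | 39.0 / 47.5 / 61.1 | 48.4 / 55.5 / 66.3 |
| 0.4 SD | 3 | 48.9 / 59.8 / 76.7 | 57.9 / 68.7 / 83.7 | 71.5 / 78.7 / 88.0 |
| 0.4 SD | 4 | 46.7 / 56.7 / 73.8 | 60.8 / 70.8 / 84.6 | 74.2 / 80.0 / 88.4 |

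Example (0.4 SD, r = 0.5, 4 categories): order costs 70.8 − 56.7 = 14.1 points; order and baseline together cost 80.0 − 56.7 = 23.3.

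With cut-points 20/40/60 and 10/40/70 added (2,500 replicates per set), the ranges are:

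- Order alone: 6.6 to 11.0 points (3 categories), 10.0 to 17.3 (4 categories).
- Order and baseline together: 11.3 to 23.1 (3 categories), 13.4 to 29.6 (4 categories).

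**5. Improved yes/no.** Chi-square power is 31.3 / 38.0 / 48.4 at 0.3 SD and 50.2 / 56.8 / 69.0 at 0.4 SD. The baseline-stratified test on the Day 5 grade gives 52.9 / 57.0 / 67.8 and 78.3 / 81.3 / 88.0. Over all cut-points the gap is 17 to 28 points.

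**6. Only if the diary holds a VAS.** Change is cut at 0/20/40 mm for the chi-square test.

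| Effect | Chi-square | t-test on change | Baseline-adjusted ANCOVA |
|---|---|---|---|
| 0.3 SD | 29.8 / 41.2 / 58.3 | 47.3 / 61.1 / 80.8 | 58.6 / 66.8 / 82.8 |
| 0.4 SD | 52.5 / 65.9 / 86.1 | 72.7 / 85.0 / 96.2 | 84.3 / 89.8 / 97.2 |

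Chi-square is 11 to 32 points below ANCOVA; 1 to 12 of these come from baseline adjustment (ANCOVA minus t-test). A closed-form check at 0.4 SD, r = 0.5:

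- √(1/154 + 1/77) = 0.1396, and the effect is 0.4 × 22 = 8.8 mm.
- ANCOVA: residual SD 22 × √(1 − 0.25) = 19.05; z = 8.8/(19.05 × 0.1396) = 3.31; power Φ(3.31 − 1.96) ≈ 91%.
- t-test: SD of change √(324 + 484 − 396) = 20.3; z = 8.8/(20.3 × 0.1396) = 3.11; power ≈ 87%.

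The simulated 89.8% and 85.0% are slightly lower, in keeping with the limits at the ends of the scale.

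**7. Other models.** Under a proportional-odds shift with odds ratio 2.0, chi-square versus Wilcoxon gives 67% versus 76% (3 categories), 64% versus 79% (4) and 59% versus 79% (5). Over odds ratios 1.5 to 2.5 the loss is about 5 to 22 points. A latent shift of 0.35 SD, with every distinct grade change kept as its own category, gives chi-square 32 / 42 / 58%, Wilcoxon 52 / 64 / 80% and a baseline-adjusted model 65 / 73 / 82%.

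**8. No effect.** In the main simulations every test rejected in 4.5% to 5.6% of replicates, so the comparison is of power at equal type I error.

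**The case against.** The strongest reply has four parts.

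- **The scale is not visible.** The text is a synopsis and points to symptom-definition tables that are not shown. They may define cough grades. If the outcome is improved yes or no, the complaint about order falls away. This stands as a limit, but the complaint then becomes one of dichotomising, and the tables would not change the named test.
- **The SAP may refine it.** Categories, day and stratification are usual SAP content, and a row-mean-score statistic is itself referred to a chi-square distribution. A SAP could therefore sharpen the test without contradicting the protocol. Even so, an unqualified chi-square test on frequencies ordinarily means the nominal, unadjusted one, and the protocol has chosen it.
- **The size depends on chosen inputs.** This stands. At r = 0.5 with 3 categories, ignoring order costs about 1 point at 0.1 SD, 10 at 0.4, 3 to 4 at 0.6 and 2 at 0.7; with 4 categories about 3, 17, 8 and 4. The range 0.3 to 0.4 SD lies near the largest gap. More categories widen it, which fits the losses of 20 to 22 points when no grade changes are merged.
- **The consequence is limited.** Randomisation balances baseline cough in expectation, so there is no bias. The yes/no and VAS comparisons also set the planned test against a different form of the outcome. Both points are fair, and the claim is confined to efficiency.

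**Conclusion.** The concern holds. The protocol commits a secondary efficacy endpoint to a test that does not adjust for baseline cough and, with three or more categories, does not use the order of severity. Both pieces of information are already in the diary.

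For effects of 0.3 to 0.4 SD at 154 versus 77, the loss is about 7 to 17 points of power from ignoring order and 11 to 30 from ignoring order and baseline together. A yes/no outcome costs 17 to 28 points against the baseline-stratified test on the Day 5 grade. The direction is the same in every model tried. The size rests on assumed effect, spread, correlation and cut-points, and shrinks for very small or large effects. This is a worthwhile, low-cost improvement and not a threat to validity.

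**What to change.** Replace the chi-square test in section X, item 4 with one that uses order and baseline, applied to one pre-specified value per subject, for example Day 5.

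- **Ordered grades:** a Cochran-Mantel-Haenszel row-mean-score test stratified by baseline cough grade, or a proportional-odds model with baseline grade as covariate.
- **VAS:** ANCOVA at Day 5, or a mixed model over the diary days, with baseline cough VAS as covariate, reporting the adjusted difference with its 95% CI.

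Keep the frequency and percentage table as description.

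The cost is the wording of one sentence, including the choice of day, since the endpoint is now stated only over the treatment period. There are no new data and no new patients. The downside is slightly more analysis work and, for the model-based options, a proportional-odds or linearity assumption.
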